9.2.1. Hematology

The following laboratory tests will be included: red blood cell count (RBC), hemoglobin, hematocrit (HCT), platelet count, mean corpuscular hemoglobin (MCH), mean corpuscular hemoglobin concentration (MCHC), mean corpuscular volume (MCV), red blood cell distribution width (RDW), WBC count, total neutrophils, lymphocytes, monocytes, eosinophils, and basophils.

Baseline values and change from baseline at each scheduled post-baseline timepoint will be descriptively summarized. All hematology data by subject will be presented in a listing, with the measurements outside of the reference range flagged.

For the schedule of hematology laboratory tests, please refer to Appendix 1.

9.2.2. Serum Chemistry

The following laboratory tests will be included: blood urea nitrogen (BUN), calcium, creatinine, sodium, potassium, chloride, magnesium, bicarbonate, protein, albumin, bilirubin (TBL), alkaline phosphatase (ALP), aspartate aminotransferase (AST), creatinine phosphokinase (CPK), and alanine aminotransferase (ALT).

Baseline values and change from baseline at each scheduled post-baseline timepoint will be descriptively summarized. All chemistry data by subject will be presented in a listing, with the measurements outside of the reference range flagged.

For the schedule of serum chemistry laboratory tests, please refer to Appendix 1.

9.2.3. Urinalysis

The following laboratory tests will be included: specific gravity, pH, protein, glucose, leukocyte esterase, and blood.

Baseline values and change from baseline at each scheduled post-baseline timepoint will be descriptively summarized. All urinalysis data by subject will be presented in a listing.

For the schedule of urinalysis laboratory tests, please refer to Appendix 1.

9.3. Vital Sign Measurements

Vital signs, to be assessed at each study visit, include temperature, HR, respiratory rate, and blood pressure (BP) after resting for at least 5 minutes. Vital signs will be obtained with the subject in the same position; BP and HR should be the mean of 3 measurements taken ≥ 5 minutes apart. BP should be taken via an automated recorder.

On Day 1 of dosing, vital signs will be taken predose and at 1 hour postdose. At all other visits, vital signs will be taken prior to dosing.

Summary tables presenting observed values and changes from baseline will be presented for vital sign data, including systolic BP (mmHg), diastolic BP (mmHg), temperature ($^{\circ}\text{C}$), pulse (bpm), and respiration (breaths/minute) for subjects in the Safety set.

Changes from baseline at each scheduled post-baseline visit will be presented. All vital sign data by subject will be presented in a listing.

9.4. Physical Examination

At Screening, Day 1, Week 12, and Week 16, a complete physical examination will be conducted including a neurological examination (gross motor and deep tendon reflexes), height (Screening only) and weight, and assessment of the following: general appearance, skin, head and neck, mouth, lymph nodes, thyroid, abdomen, musculoskeletal, cardiovascular, neurological, and respiratory systems. At all other visits, an abbreviated cardiopulmonary physical examination will be conducted, with other systems assessed as directed by interval history.

Physical examination results will be presented in a listing.

9.5. Electrocardiogram

Triplicate ECG recordings will be obtained at each scheduled timepoint and the average of the three readings will be used to determine ECG intervals, including QRS, heart rate, PR, QT, Corrected QT interval using Fridericia's formula (QTcF), Corrected QT interval using Bazett's formula (QTcB) and RR. Missing ECG data will not be imputed. If one or two replicates are missing, the average will be calculated on the available replicates.

ECG Numeric Variables

HR, PR, QRS, QT, QTcF, QTcB, and RR will be summarized using descriptive statistics. The change from baseline of these ECG parameters at each timepoint will be listed for each subject. For each timepoint of measurement, the changes from baseline will be summarized using descriptive statistics.

Categorical Analysis

The cumulative incidence count and percentage of subjects with any postdose QTcF values of > 450 msec, > 480 msec, and > 500 msec will be tabulated for all subjects. Subjects will be listed with corresponding baseline values, Δ QTcF, and baseline and treatment HR. The cumulative incidence count and percentage of subjects with Δ QTcF increase of > 30 msec and > 60 msec will be tabulated. Also subjects with QTcB/QTcF >480 ms and/or change from baseline in QTcB/QTcF >60 ms will also be listed in a separate listing.

Morphology Findings

New ECG morphologies for each subject not present on any ECG at baseline for that subject will be summarized for all observation timepoints combined.

The number and percentage of subjects having new morphology changes from baseline will be reported, and summarized as QTc Prolongation, ST depression, ST elevation, T-waves biphasic, T-waves flat, T-wave inversion, or U-wave abnormality.

ECG overall interpretation by visit will be presented in a listing.

For the schedule of ECG test, please refer to Appendix 1.

10. Pharmacokinetics

Blood samples for plasma PK analysis of MYK-461 will be collected within 2 hours prior to dosing at the following timepoints: Day 1, Week 1, Week 2, Week 3, Week 4, Week 5, Week 6, Week 7, Week 8, Week12 and Week 16 or End of Study (End of Treatment + 4 Week) for Part A and Part B.

Concentrations that are BLQ will be treated as zero for descriptive statistics. All missing concentrations will be treated as missing for descriptive statistics.

Plasma concentration data of MYK-461 will be listed by subject and summarized by MYK-461 dose level and nominal time point using descriptive statistics (number of subjects (n), arithmetic mean, standard deviation (SD), coefficient of variation (CV%), geometric mean, geometric CV%, median, minimum, and maximum).

Arithmetic mean plasma concentration data of MYK-461 versus nominal time (days) will be plotted by MYK-461 dose level on linear and semi-logarithmic scales. Individual plasma concentration data of MYK-461 versus actual times will also be presented on linear and semi-logarithmic scales. Overlay plot of individual plasma concentration data of MYK-461 versus actual times will also be presented on linear and semi-logarithmic scales.

11. PK-QTc Analyses

A concentration-QTc regression analysis, based on data collected from the ECG recordings after drug administration and MYK-461 concentration values for each subject at each matching timepoint will be performed. A linear mixed effects (LME) model will be fitted on change from

baseline QTcF, with baseline QTcF, MYK-461 concentration as an independent variable and subject as a random effect. Baseline QTcF is defined as the average of the last assessment prior to start of study treatment. A corresponding scatter plot will be provided. The analyses will be performed on PK/ECG set.

12. Pharmacogenomic/HCM Genotype

For all subjects who provide consent, blood will be drawn on prior to dosing Day 1 for assessment of HCM genotype and potentially additional deoxyribonucleic acid (DNA) sequencing.

In addition, subjects may consent separately to collection of pharmacogenetic samples that will be stored for potential future analysis of genetic biomarkers of efficacy, safety-related, PD, or PK parameters as determined by future studies using clinically meaningful endpoints, through DNA sequencing or other genetic testing.

Data collected for Pharmacogenomic and HCM Genotype will be listed and summarized as requested by the sponsor.

13. Interim Analysis

There will be an interim analysis for Part A subjects, when the last subject for Part A completes the study. The Part A interim analysis will include: demographics, disposition, adverse events, drug exposure, vital signs, laboratory evaluations, ECG, PK, primary and secondary efficacy endpoints.

14. Changes in the Planned Analysis

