5.3 Exclusion Criteria

Subjects who meet any of the following criteria will be excluded from the study.

1. Hypersensitivity to MYK-461 or any of the components of the MYK-461 formulation.
2. Presence of any medical condition that precludes exercise stress testing.
3. History of sustained ventricular tachyarrhythmia.
4. History of syncope with exercise within past 6 months.
5. Active infection.
6. Persistent atrial fibrillation or atrial fibrillation at Screening or history of paroxysmal atrial fibrillation with resting rate documented >100 bpm within 1 year of screening.
7. Has QTc Fridericia (QTcF) > 500 ms, or any other ECG abnormality considered by the investigator to pose a risk to subject safety (e.g., second degree atrioventricular block type II).
8. Aortic stenosis or fixed subaortic obstruction.
9. History of LV systolic dysfunction (LVEF < 45%) at any time during their clinical course.

10. History of obstructive coronary artery disease (stenosis of >70% of luminal diameter in one or more coronary arteries).
11. History of malignancy of any type, with the following exceptions: in situ cervical cancer more than 5 years prior to Screening or surgically excised non-melanomatous skin cancers more than 2 years prior to Screening.
12. Positive serologic test at Screening for infection with human immunodeficiency virus (HIV), hepatitis C virus (HCV), or hepatitis B virus (HBV).
13. Positive test for alcohol or drugs of abuse at Screening.
14. History or evidence of any other clinically significant disorder, condition, or disease (with the exception of those outlined above) that, in the opinion of the investigator or MyoKardia physician, would pose a risk to subject safety or interfere with the study evaluation, procedures, or completion.
15. Participated in a clinical trial where the subject received any investigational drug (or is currently using an investigational device) within 30 days prior to Screening, or at least 5 times the respective elimination half-life (whichever is longer).
16. Current use of tobacco- or nicotine-containing products exceeding 10 cigarettes per day or equivalent.
17. Part A: Subjects who in the opinion of the investigator require ongoing therapy with β -blockers, calcium channel blockers, or disopyramide. Subjects on any of these medications who, in the opinion of the investigator, can safely be withdrawn are eligible as long as medication is discontinued at least 14 days prior to the Screening visit.

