11.3.8.1 Adverse Events

AEs will be mapped to system organ classes and preferred terms using the Medical Dictionary for Regulatory Activities (MedDRA). AEs will be monitored during the study and the data analyzed with respect to overall incidence as well as severity and potential relationship of AEs to study medication. AEs with onset on or after the first dose of study medication, or with an onset before the first dose of study medication that increase in severity on or after the first dose of study medication, will be considered treatment-emergent. Treatment-emergent AEs will be summarized for the Safety Analysis Population by system organ class and preferred term, and by severity and relationship to treatment. Severe and life-threatening AEs, SAEs, and AEs leading to study withdrawal, if any, will be presented in data listings.

11.3.8.2 12-lead Electrocardiogram

The RR, PR, QRS, and QT intervals will be measured. HR will be calculated as $60/(RR \times 1000)$ (with RR expressed in msec) and rounded to the nearest integer.

Correction for Heart Rate

Corrected QT interval (QTc) will be calculated using the manually over-read QT values. Each individual ECG QT value will be corrected for HR. The measured QT data will be corrected for HR using the Fridericia method (QTcF) as per the following formulae/method (with QT, RR and QTc expressed in msec):

Fridericia's Correction:

$$QT_{cF} = \frac{QT}{(RR / 1000)^{1/3}}$$

ECG Numeric Variables

HR, PR, QRS, and QTcF will be summarized using descriptive statistics. The change from baseline of these ECG parameters at each timepoint will be listed for each subject. For each timepoint of measurement, the changes from baseline will be summarized using descriptive statistics.

Categorical Analysis

The incidence count and percentage of subjects with any postdose QTcF values of > 450 msec, > 480 msec, and > 500 msec will be tabulated for all subjects. Subjects with QTc values > 500 msec will be listed with corresponding baseline values, Δ QTcF, and baseline and treatment HR. The incidence count and percentage of subjects with Δ QTcF increase of > 30 msec and > 60 msec will be tabulated.

Morphology Findings

New ECG morphologies for each subject not present on any ECG at baseline for that subject will be summarized for all observation timepoints combined.

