All analysis and summary tables will have the analysis population sample size (i.e., number of subjects) in the column heading. All listings will be sorted for presentation in order of study site, subject identification and date of procedure or event.

The day of the first dose of study drug will be defined as Day 1.

Baseline value will be defined as the last non-missing value in date/time before the first dose of study drug is administered.

Missing data handling will be described in Section 7, 8, 9 and 10.

All laboratory data will be reported using International System of Units (SI).

The planned analysis visit window for weekly visits will consider +/- 3 days of the scheduled visit date based on the date of first exposure to the study drug. For a missed visit, the evaluation will be rescheduled as close as possible to the original planned visit, thus analysis windows have been designed to be all-inclusive. If more than one result is available for a particular visit window and results are equidistant from the analysis target date, the later result will be selected to break the tie. The associated visit window with corresponding visit is tabulated below.

Visit	Scheduled Visit Day	Visit Window
Day 1	Day 1	[1, 4]
Week 1	Day 8	[5, 11]
Week 2	Day 15	[12, 18]
Week 3	Day 22	[19, 25]
Week 4	Day 29	[26, 32]
Week 5	Day 36	[33, 39]
Week 6	Day 43	[40, 46]
Week 7	Day 50	[47, 53]
Week 8	Day 57	[54, 64]
Week 10*	Day 71	[65, 78]
Week 12*	Day 85	[79, 99]
Week 16	Day 113	[100, 116]

*CPET may be conducted between study visits 10 and 12, therefore the planned analysis window ranges from Day 65 to Day 99 with Day 85 set to the scheduled visit day. Note: The window is adjusted for visit 12; visit 10 will not be presented.

For any subjects who discontinued treatment prior to Week 4 dose adjustment, the subjects will not be presented in the treatment columns (initial dose/adjusted dose), however will be presented in the total column in the table.

If the “seconds” portion of the date/time variable is missing or not collected, it will be imputed as “:00”, as needed.

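### The QTcF threshold counts are called incidence but take no account of baseline, so subjects who enter above 450 or 480 ms are counted with new cases

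*SAP*

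**What the plan says.** **Entry.** Protocol section 5.3, exclusion 7, reads "Has QTc Fridericia (QTcF) > 500 ms, or any other ECG abnormality considered by the investigator to pose a risk to subject safety". On the numerical limit alone, a QTcF of 451 to 500 ms is eligible.

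**Threshold counts.** SAP section 9.5 (Categorical Analysis) states: "The cumulative incidence count and percentage of subjects with any postdose QTcF values of > 450 msec, > 480 msec, and > 500 msec will" appear in a table that covers every subject. Protocol section 11.3.8.2 sets the same rule: "The incidence count and percentage of subjects with any postdose QTcF values of > 450 msec, > 480 msec, and > 500 msec". Neither text restricts the count to subjects at or below the threshold at baseline. The SAP's list of tables gives the output as Table 14.3.5.2 (one version per part, Safety Set) and names no QTcF shift table.

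**Where baseline does enter.** SAP section 4 defines it: "Baseline value will be defined as the last non-missing value in date/time before the first dose of study drug is administered". Section 9.5 then uses it in several places:

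- A listing: "Subjects will be listed with corresponding baseline values", with the change in QTcF and the heart rates.
- Separate change categories: "QTcF increase of > 30 msec and > 60 msec will be tabulated".
- Descriptive summaries of change from baseline at each timepoint.
- A morphology summary limited to new findings: "New ECG morphologies for each subject not present on any ECG at baseline for that subject will be summarized". One of its categories is QTc prolongation, with no threshold given.

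SAP section 11 adds a concentration-QTc model for change in QTcF, adjusted for baseline QTcF.

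**The concern.** Incidence normally means new cases. The threshold table as specified counts every subject with a value above the limit after the first dose, including those who were above it before dosing. A subject who enters at 460 ms and does not change is a > 450 ms case. One who enters at 485 ms and does not change is both a > 450 ms and a > 480 ms case.

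The study is open-label with no control arm, so no concurrent group shows how many such cases would arise without the drug. Each part has about 10 subjects, and one pre-existing case moves the percentage visibly. The same section of the SAP applies the new-onset principle to ECG morphology but not to the QTcF thresholds. ECG results also go into the Part A interim analysis (SAP section 13), so the table may be read before the study is complete.

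**Working it through.** The documents state no expected QTcF frequency, so there is no figure of theirs to reproduce.

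**1. Number of postdose timepoints.** Day 1 at 1 hour postdose gives 1. Weeks 1 to 8 give 8. Weeks 12 and 16 give 2. The total is 1 + 8 + 2 = 11 (Protocol sections 4 and 9.3.3; SAP section 3.1 and Appendix 1). Here postdose means any ECG after the first dose. The Week 16 ECG is off drug, and neither document says whether it counts.

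**2. Chance that an unchanged subject is counted.** Assume visit means vary independently and symmetrically about a stable level. For a stable level exactly at the threshold, each visit exceeds it with probability 0.5:

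P(at least one of 11 above) = 1 − 0.5^11 = 1 − 1/2048 = 0.9995

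This does not depend on the visit SD, and a stable level above the threshold gives a higher probability. Without Week 16 it is 1 − 0.5^10 = 0.9990. Positive correlation between visits, or early withdrawal, would lower it.

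**3. Weight of one subject.** With about 10 subjects per part (SAP section 4.1), 1/10 = 10 percentage points. SAP section 4 makes the default columns combinations of initial and adjusted dose, so the share within a column can be larger.

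**4. Can the change counts supply the number of new cases?** Compare two subjects:

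| Baseline to worst postdose | Change | > 450 count | Change > 30 count | New > 450? |
|---|---|---|---|---|
| 445 to 470 ms | +25 | 1 | 0 | yes |
| 460 to 460 ms | 0 | 1 | 0 | no |

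Both contribute identically to the two planned tabulations, yet only one is a new exceedance. In the other direction, a subject going from 455 to 490 ms (+35) appears in both the > 450 and the change > 30 counts and is not a new > 450 ms case. The two sets of counts are not crossed, so they cannot give the number of new cases.

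**5. Effect on the reported figure.** Suppose one part of 10 holds both subjects in the table and the other eight stay at or below 450 ms throughout. The planned row reads 2/10 = 20%. New exceedance reads 1/9 = 11.1%, with 1/10 already above at baseline.

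**6. Illustrative range, no drug effect.** The inputs are assumptions, not figures from the documents: mean QTcF 420 to 450 ms, between-subject SD 20 to 25 ms, visit SD 8 to 12 ms, entry at 500 ms or less, 11 timepoints.

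| Threshold | Counted under the planned rule | Share of those already above at baseline | New exceedance among those at or below at baseline |
|---|---|---|---|
| > 450 ms | 20% to 81% | 30% to 70% | 13% to 64% |
| > 480 ms | 1% to 31% | 13% to 43% | 0.8% to 23% |

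The ranges are too wide to predict this trial. The last column is not zero even with no drug effect, because repeated measurement takes subjects near a limit across it by chance.

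**The case against.** The strongest reply is that the stated safety endpoint is change from baseline in ECGs (Protocol section 11.2.4; SAP section 3.2.4), and the rest of section 9.5 serves that endpoint. The threshold count is a descriptive supplement with no test, stopping rule or decision attached. With about 20 subjects, a reader can match each counted case to its baseline in the listings. Exclusion 7 also lets the investigator exclude other ECG abnormalities, so entry at 451 to 500 ms is possible but not assured.

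Most of this stands, and it limits the point to tabulation and labelling. Matching by hand is less convenient than it sounds, however. The dedicated outlier listing (16.2.12.2) starts at > 480 ms or a change > 60 ms, so many > 450 ms cases fall outside it. Both ECG listings are on the Efficacy Set, while the table is on the Safety Set.

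A reader might infer more than the documents support:

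- *That the ECG plan ignores baseline.* It does not; only the threshold table does.
- *That the counts reflect the entry limit rather than the drug.* They depend on both.
- *That Part A and Part B will differ for this reason.* The same criterion applies to both parts, the documents give no baseline QTcF by part, and Protocol section 11.3.2 rules out a statistical comparison of effect sizes.
- *That near-limit subjects show the size of the defect.* A subject stable 10 ms below a threshold crosses it at least once with probability 1 − Φ(10/SD)^11, which is 0.22 at an assumed visit SD of 5 ms and 0.96 at 15 ms. Such a subject usually has a baseline at or below the limit and would still count as new after the fix.

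**Conclusion.** The point holds as a defect of tabulation and labelling. The > 450 and > 480 ms rows mix pre-existing with new cases, and the other planned tabulations do not give the number of new exceedances. An unchanged subject whose level is at or above a limit is almost certain to be counted (0.9995 under independent visits and a full set of 11 ECGs) and adds about 10 percentage points in a part of about 10. The > 500 ms row is largely protected by exclusion 7.

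The number of subjects affected is unknown, because the documents give no QTcF distribution. The individual data are collected, so nothing is lost. The point does not question the entry limit itself. Importance is low to moderate.

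**What to change.** In SAP section 9.5 and Table 14.3.5.2:

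1. Tabulate baseline QTcF category (≤ 450, > 450 to 480, > 480 to 500, > 500 ms) by worst postdose category.
2. For each threshold, report the number and percentage with a new exceedance, using subjects at or below that threshold at baseline as the denominator. Show the number already above it alongside.
3. Keep the all-subject count as a secondary row, not labelled as incidence.
4. State whether the off-drug Week 16 ECG counts as postdose.
5. Note that new exceedances still include chance crossings by subjects near a limit, and should be read with the > 30 and > 60 ms change counts.

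The cost is a change of table layout and slightly smaller denominators. No new data, visits or subjects are needed.

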APPENDIX 1 SCHEDULE OF STUDY PROCEDURES

Timepoint (Day/Week) ^a	Screen D -28 to D -1	D1	W1	W2	W3	W4	W5	W6	W7	W8	W12/ ET	W16/ EOS or ET + 4W
General Procedures												
Informed consent	X											
Medical history ^b	X											
Telephone call to subject ^c		←→								←→		
Vital signs ^d	X	X	X	X	X	X	X	X	X	X	X	X
AEs/SAEs ^e	X	X	X	X	X	X	X	X	X	X	X	X
Concomitant therapy	X	X	X	X	X	X	X	X	X	X	X	X
Physical examination ^f	X	X	X	X	X	X	X	X	X	X	X	X
Body height	X											
Body weight	X	X									X	X
ECG ^g	X	X	X	X	X	X	X	X	X	X	X	X
Resting TTE ^h	X	X	X	X	X	X	X	X	X	X	X	X
CPET ⁱ		X									X ^j	
Hemodynamic stress echocardiography ^k	X					X					X	X
Optional pulse wave optical biosensor ^l	X	X	X	X		X				X	X	X
Apply cardiac monitoring skin patch ^m	X	X		X		X		X		X ⁿ	X	
Retrieve previously applied cardiac monitoring skin patch ^m		X		X		X		X		X	X	X
Laboratory												
Hepatitis panel, HIV test, TSH, and drug/alcohol testing	X											
PK samples ^o		X	X	X	X	X	X	X	X	X	X	X
Chemistry	X	X				X				X	X	X
Hematology	X	X				X				X	X	X
Urinalysis	X	X									X	X

Footnotes and abbreviations defined on last page of table.

- ^d Vital signs include temperature, HR, respiratory rate, and BP after resting for at least 5 minutes. Obtain vital signs with subject in the same position; BP and HR should be the mean of 3 measurements taken ≥ 5 min apart. BP should be taken via an automated recorder. On Day 1, vital signs will be taken predose and at 1 hour postdose. At all other visits, vital signs will be taken predose.
- ^e Any changes in baseline conditions that occur after the ICF is signed are recorded on the medical history eCRF, unless the change is related to a study procedure, in which case it is considered an AE. All changes that occur after the administration of the study medication are recorded as AEs.
- ^f At Screening, Day 1, Week 12, and Week 16, a complete physical examination will be conducted including a neurological examination (gross motor and deep tendon reflexes), height (Screening only) and weight, and assessment of the following: general appearance, skin, head and neck, mouth, lymph nodes, thyroid, abdomen, musculoskeletal, cardiovascular, neurological, and respiratory systems. At all other visits, an abbreviated cardiopulmonary physical examination will be conducted, with other systems assessed as directed by interval history.
- ^g A 12-lead ECG (triplicate) will be performed after 10 minutes of rest at Screening and at all study visits. On Day 1, ECG will be performed within 2 hours predose and at 1 hour postdose. At all other visits, ECGs will be taken predose.
- ^h Instantaneous peak LVOT gradient (baseline) and provoked peak LVOT gradient (Valsalva maneuver) will be assessed. Ejection fraction (2-dimensional and 3-dimensional), LVFS, global longitudinal strain by speckle tracking, and VTI will be analyzed. Resting TTE should be performed prior to hemodynamic stress echocardiography or CPET.
- ⁱ CPET after a 4-hour fast (water is allowed) by standardized treadmill with assessment of LVOT peak gradient. CPET should be conducted prior to dosing with study medication. The following will be assessed: VO_2 , VCO_2 , VE, VE/VO_2 , VE/VCO_2 , and respiratory exchange ratio (RER).
- ^j CPET may be conducted at the Week 12 visit or anytime between Weeks 10 and 12. If CPET and hemodynamic stress echocardiography are conducted at the same visit, the hemodynamic stress echocardiography should be conducted first, followed by the CPET.
- ^k Subjects will undergo a standard symptom-limited exercise test. Instantaneous peak LVOT gradient will be assessed immediately post-exercise by TTE. Post Screening, hemodynamic stress echocardiography should be conducted prior to dosing with study medication.
- ^l For participating sites, an optical biosensor may be fastened to the subject's wrist for several minutes to collect data on pulse wave morphology. This assessment is optional and will be conducted only if the subject provides consent.
- ^m The cardiac monitoring adhesive skin patch is to be applied at Screening visit and removed at the Day 1 visit. Additional patches should be applied and retrieved at the timepoints shown. Each subject should be trained on applying the patch and should be provided with an additional patch for the subject to apply if a patch comes off after less than 14 days.
- ⁿ At Week 8, the subject should be provided with an additional cardiac monitoring skin patch. At Week 10, the subject is to remove the patch applied at Week 8 and mail the patch using a preaddressed, postage-paid envelope. The subject will then apply the additional patch that was supplied at Week 8.
- ^o Collect PK samples ≤ 2 hours prior to dosing.
- ^p FSH testing at Screening for postmenopausal women to confirm postmenopausal status.
